Table 3. Under the null (Scenario #0), the adaptive design controls the total Type 1 error below 2.5%, stops early for futility 63% of the time, and the average number of randomizations is 361. If the effect is uniform across cells (scenario #1), the fixed-sample design is optimal, but the adaptive design results in only a small loss of power (from 89 to 80%). The adaptive design performs much better (higher power and smaller expected sample size) than the fixed sample, conventional trial when the effect size distribution across the subgroups is in accord with the biological assumptions (scenarios #2 and 3). If the effect is concentrated in two cells with small core volumes (scenario #3), the adaptive design maintains power (87%) while the conventional design collapses (41% power). The adaptive design also performs well compared to a non-adaptive, fixed sample that includes efficient multiple comparisons-adjusted testing for effect in subgroups at the end of the study. (see Lai et al⁵⁹)

Secondary analysis: Our secondary endpoint is the proportion of patients with mRS 0-2 at day 90 (indicating functional independence). The difference in the proportions of patients with mRS 0-2 between treatment arms will be assessed using logistic regression.

Subgroup analyses: Subgroup analyses of the effect of endovascular therapy on the primary and secondary endpoints will be performed. Subgroups will be defined based on the stratification variables, key demographic factors (such as race and ethnicity), tPA vs. no tPA, CTP vs. MRI selection, and witnessed vs. unwitnessed symptom onset, wake-up vs non-wake-up stroke, and TIC1 0-2a vs. TIC1 2b/3 results in cath lab.

Missing data/lost to follow-up (LTFU):

All effort is put forth to ensure near complete follow-up, in particular with the assessment of the primary outcome (mRS at 90 days), death (mRS=6), and stroke recurrence. If the primary outcome (mRS at 90 days) cannot be assessed in the clinic, it will instead be obtained by phone using a structured interview. If the subject’s mRS cannot be obtained in clinic or by phone within the window of 60 to 120 days from randomization, then for primary analyses the day 30 mRS score will be used as the primary outcome (ie day 30 mRS carried forward). If neither the 30-day nor the 90-day mRS is available, then the mRS will be imputed. We do not expect this to alter the main study results given our estimated very low LTFU rate (<2%).

DEFUSE 3 Timetable

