Based on previous experiences with acute stroke trials, it is anticipated that there will be minimal loss to follow up for the 90-day assessment of the primary outcome. In the IMS I Trial, only 1 of 80 (1.25%) subjects were LTFU. In the IMS II Pilot Study, 2 of 73 (2.7%) were LTFU. In the IMS III Study, 27 of 656 (4.1%) subjects were LTFU. In SWIFT-PRIME, 4 of 191 (2.1%) were LTFU. In Fast-Mag, out of 1700 patients, 4 patients (0.2%) did not have at least day 30 follow-up.

~~In DEFUSE 3, at each analysis stage, the definitive sample for the boundary crossing analysis will consist of the first N consecutively recruited subjects, where N is the design specified sample size at each interim stage or the total sample at the final stage, who are in the selected subgroup if one has been chosen. All effort is put forth to ensure near complete follow-up, in particular with the assessment of the primary outcome (mRS at 90 days), death (mRS=6), and stroke recurrence. If the primary outcome (mRS at 90 days) cannot be assessed in the clinic, it will instead be obtained by phone using a structured interview. The final analysis will be conducted when all subjects in the analysis sample have reached the upper limit of the window for the 90-day outcome (120 days after randomization), and when the coordinating center believes it has exhausted all reasonable efforts to obtain outcome data collected within the window but delayed in data entry.~~

Missing 90-day mRS data (no mRS available within a 60-120 day window) will be handled by a hybrid approach: if the 30-day mRS is available, it will be “carried forward”, if not, the 90-day mRS will be “multiply imputed” (multiple imputation) using 'age' and 'NIHSS score at hospital discharge' as predictor variables.

All final analyses described in the SAP will use the multiple imputation data if applicable. ~~Specifically, the standardized, multiple imputation adjusted Wilcoxon rank sum statistic will be calculated. The Kullback-Leibler score, used in the~~

~~adaptive design for subgroup selection, will also be estimated using multiple imputation data. (see section 9.2)~~

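### A missing 90-day mRS is replaced by the day-30 score as if it had been observed, while the planned multiple imputation is kept for patients without a day-30 score and leaves out treatment arm

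*Protocol*

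**What the plan says.** Protocol 3.8, under missing data and loss to follow-up, applies when the score "cannot be obtained in clinic or by phone within the window of 60 to 120 days from randomization". In that case "then for primary analyses the day 30 mRS score will be used as the primary outcome". Only when both scores are absent does the next step apply: "If neither the 30-day nor the 90-day mRS is available, then the mRS will be imputed".

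SAP Section 8, which governs the final analysis, keeps the same order: "Missing 90-day mRS data (no mRS available within a 60-120 day window) will be handled by a hybrid approach". The day-30 score is carried forward if there is one. Otherwise the 90-day score is multiply imputed "using 'age' and 'NIHSS score at hospital discharge' as predictor variables". The SAP applies this to all its final analyses, so the dichotomised mRS 0-2 outcome is treated in the same way as the shift analysis.

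The protocol expects loss below 2% and no effect on the main result. Neither document plans a sensitivity analysis that would test this.

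**The concern.** Carry-forward treats the day-30 grade as the day-90 grade. It allows for no recovery, decline or death after day 30, and it enters the rank test with the same certainty as an observed score.

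The order of the two methods is also the wrong way round. Multiple imputation, which does carry uncertainty, is reserved for the patients about whom least is known. Patients with a 30-day score on the same scale get a single fixed value, although that score could serve as a predictor. The imputation model also omits treatment arm, so it draws the imputed scores towards a common distribution and slightly dilutes any real difference.

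Acute treatment is open-label (SAP Section 7), so loss need not be equal in the two arms. What is at stake is a small bias in the primary comparison, whose direction depends on which arm loses patients.

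**Working it through.** **Inputs.** Projected 90-day mRS 0 to 6 (Protocol 3.8, SAP Section 10): endovascular 18.0, 11.5, 19.6, 11.5, 16.4, 11.5, 11.5%; medical 9.7, 7.9, 15.0, 17.7, 14.4, 17.7, 17.7% (sums to 100.1, rescaled to 100). Fixed design: 188 per arm, 90% power, 5% two-sided. Loss: under 2% (Protocol 3.8); 4.1% is the highest rate among the trials cited in SAP Section 8. Randomized at the halt: 182 (SAP Section 2).

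**The plan's own figure.** Let p be the probability that an endovascular patient has the better score, counting ties as half, and let T = 1 − Σ(mean category proportion)³. Then n per arm = T(1.960 + 1.282)² / [6(p − 0.5)²].
- The table gives p = 0.5953 and T = 0.978.
- n = 0.978 × 10.51 / (6 × 0.0953²) = 188.7, against 188 in the plan.
- Power = Φ(√(6n/T)·(p − 0.5) − 1.960). At n = 188 this is Φ(3.236 − 1.960) = 89.9%. The planned sample size is reproduced.

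**How many patients the rule can reach.**
- 182 × 0.02 = 3.6, so fewer than 4.
- 182 × 0.041 = 7.5, so about 7.
- At the planned maximum of 476: 9.5 and 19.5.

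These are upper limits, because some lost patients will also lack a day-30 score and would be multiply imputed. The 0.2% rate in SAP Section 8 is not a usable lower limit: it counts patients without even day-30 follow-up, to whom carry-forward cannot apply.

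**Effect on power.** Assumption: in survivors the carried-forward score is one grade worse than the true day-90 score, capped at 5. A fraction f of an arm is replaced by this shifted distribution and power is recomputed at 188 per arm, 5% two-sided.

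| Overall loss | Where it falls | p | Power |
|---|---|---|---|
| none | – | 0.5953 | 89.9% |
| 2% | both arms equally | 0.5951 | 89.8% |
| 4.1% | both arms equally | 0.5948 | 89.6% |
| 2% | all endovascular (4% of that arm) | 0.5911 | 87.1% |
| 4.1% | all endovascular (8.2% of that arm) | 0.5866 | 83.7% |
| 2% | all medical | 0.5991 | 92.0% |
| 4.1% | all medical | 0.6031 | 93.8% |

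With 91 per arm (182 split evenly) and the revised one-sided level of 0.023, balanced loss moves power from 60.1% to 59.9% (2%) or 59.7% (4.1%).

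**Deaths between day 30 and day 60.** To bound the wording gap discussed under objection, assume that 10 to 30% of projected deaths fall on days 31 to 59 and are scored at a living grade. That is 1.0 to 3.1 endovascular and 1.6 to 4.8 medical patients of 182. At 188 per arm, power stays at 89.9% if they are scored 5, and becomes 89.5 to 88.8% if they are scored 4.

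**The case against.** The strongest defence is that a pre-specified carry-forward, with multiple imputation behind it, is a reasonable choice when under 2% of outcomes are expected to be missing, and that imputing the same few patients differently would change almost nothing. On size this stands: the balanced cases above move power by a fraction of a point. It does not explain why day-30 mRS and treatment arm stay out of an imputation model that the plan already needs, or why the statement that results will not change is left untested.

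A reader might infer that the plan scores a patient who dies on day 31 to 59 as alive, because such a patient has no mRS dated within days 60 to 120. The documents do not support this as a planned rule. Protocol 3.8 lists what follow-up must capture, "in particular with the assessment of the primary outcome (mRS at 90 days), death (mRS=6), and stroke recurrence", and so equates death with grade 6. Serious adverse events, which include death, are recorded through day 90 (Protocol 3.11), and 90-day mortality is a monitored safety endpoint (SAP 13.1). A known death is therefore a known score. What remains is a gap in wording: the SAP trigger has no explicit exception for death, and the matching SAP sentence on death sits in text marked as deleted.

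A reader might also count the early interim analysis, where everyone still in follow-up took the day-30 score. That is a separate rule (SAP Sections 2 and 9.4). The analysis is repeated on the locked database, and the manuscript reports that repeat. The documents do not say how many patients the interim rule covered.

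**Conclusion.** The concern holds for the final primary analysis as a choice of method with a small expected effect. The day-30 score stands in for the outcome with no allowance for later change or for uncertainty, although a better method is already in the plan and needs only two more predictors.

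Reach is fewer than 4 of 182 patients at the protocol's own loss rate and at most about 7 at 4.1%. Under the one-grade assumption, power at 188 per arm falls by about 0.1 to 0.3 points if loss is balanced. Larger changes, between a loss of 6.2 points (89.9 to 83.7%) and a gain of 3.9 points (89.9 to 93.8%), need all the loss to fall in one arm. The loss rate and the size of the shift are assumptions that the documents cannot confirm. No stated sample size or significance level changes.

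The treatment of deaths before day 60 is a point to clarify, not an error in the planned analysis. A death that stays unknown in a patient lost after day 30 is a different matter. Carry-forward must score that patient as alive, whereas imputation fitted to data that include deaths gives grade 6 some probability.

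**What to change.** In SAP Section 8:

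1. Multiply impute all missing 90-day mRS scores, with day-30 mRS (where available), treatment arm, age and discharge NIHSS as predictors.
2. Keep day-30 carry-forward as a named sensitivity analysis of the primary outcome.
3. State that a known death on or before the 90-day assessment is scored mRS 6 whatever its date, and so does not trigger the missing-data rule. A patient assessed alive at the 90-day visit keeps that score.

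Align the paragraph in Protocol 3.8 with this wording. The cost is a change of text, slight extra analysis work, since multiple imputation is already planned, and marginally wider intervals. No new data are needed.

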3.9. Risk analysis

Description and analysis of all increased risks to the research subjects:

Potential complications of MRI scan include localized twitching sensation due to the magnetic field changes during the scan, anxiety due to claustrophobia and allergic reaction to the contrast agent. The allergic reaction may include headache, nausea, rash, hives, nasal congestion, sneezing, itching or swelling. If a severe reaction occurs, swelling of the throat, chest tightness, or a marked drop in blood pressure may occur. In addition, pain, bleeding, bruising, coldness or inflammation at the injection site may occur. Precautions will be taken for early detection and rapid treatment if such reactions occur.

Potential complications of CT scan include radiation exposure and allergic reaction to CT contrast agents.

Radiation doses:

Combined scanning with comprehensive stroke imaging, which includes a noncontrast head CT scan, perfusion imaging, and CT angiography of the cervicocranial vessels starting at the aortic arch results in a dose of approximately 7-10 mSv. (AJNR 2010 31: 1003-1009). According to the National Council on Radiation Protection and Measurement, the average annual radiation dose per person in the U.S. is 620 millirem (6.2 milliSieverts).

Reactions to contrast agents:

- **Mild**
Nausea, Vomiting, Headache, Cough, Nasal stuffiness, Altered taste, Flushing, Itching, Rash, Hives, Sweats, Swelling of eyes or face
- **Moderate**
Mild hypotension, Tachycardia or Bradycardia, Bronchospasm, Wheezing, Dyspnea, Laryngeal edema, Generalized or diffuse erythema
- **Severe**
Cardiopulmonary arrest, Clinically manifested arrhythmias, Profound hypotension, Convulsions, Unresponsiveness, Respiratory failure, Laryngeal edema
The rate of major reactions (e.g., anaphylaxis, death) is very low, estimated at one in 170,000 administrations.

Potential complications of endovascular therapy include stroke; new clot in an artery; total blockage of an artery; infection and pain in the region of insertion site; lack of blood flow to the brain; rupture or puncture of an artery; significant tearing of the vessel wall; bleeding requiring blood transfusion; allergic reaction to contrast dye; abnormal low blood pressure requiring treatment; temporary closing of the artery (vessel spasm); formation of or dislodgments of clots which block the arteries (embolism). In rare circumstances, the procedure could result in death. At the puncture site in the groin, a blood clot or other blood vessel injury may occur and require blood transfusion or surgical repair. Infection may occur at the puncture site; this could cause pain and require additional medications. There is some chance of an allergic reaction to the x-ray contrast (dye) used during the angiogram procedure. Minor allergic reactions may include a rash or hives. There is also the possibility of a serious allergic reaction that could include shortness of breath and swelling, drop in

blood pressure, and even death. Patients will be closely monitored for these reactions and receive prompt treatment to reverse any allergic reactions.

Safety of endovascular therapy beyond 8 hours

Mechanical thrombectomy devices have been used beyond 8 hours of stroke onset in a number of clinical trials and registries. No safety concerns have been associated with late window therapy. In DEFUSE 2³⁷, patients were treated up to 12 hours after symptom onset, and no safety concerns were identified in any time window. Based on both favorable safety data and encouraging efficacy data, Stryker Neurovascular has initiated the DAWN Study with a 24 hour treatment window. No safety issues have been identified to date in DAWN. The DAWN study is being run under an FDA IDE.

Methods to mitigate risks to subjects in the trial

Methods to mitigate risks to subjects in the trial include exclusion of subjects with bleeding disorders and selection of subjects via neuroimaging (infarct core lesions less than 70 ml) to minimize the risk of symptomatic intracranial hemorrhage. Computed Tomography (CT) scans will be performed for neurological deterioration (≥ 4 point increase in National Institutes of Health Stroke Scale (NIHSS) score) to identify new strokes, hemorrhage, or edema. Hospitals will follow their local standard of care safety procedures in order to reduce the risk of kidney dysfunction caused by contrast agents. Only investigators who are trained and experienced with use of the devices allowed within the trial are eligible to participate (see **Site Approval and Monitoring Plan**) above. The adaptive design will eliminate subgroups with an unfavorable therapeutic response.

Patients will be carefully screened for CT, MRI and endovascular treatment contraindications according to the inclusion/exclusion criteria and excluded from enrollment if any are present.

Radiation exposure: Radiation exposure during all tests will be minimized by optimizing the imaging protocols and by limiting fluoroscopy-time during the endovascular procedure. All CT sequences, including the CTP sequence, meet all FDA guidelines for radiation exposure.

Stopping rules or safety triggers for the study

Symptomatic ICH or death rates that exceed pre-specified thresholds will trigger a meeting of the DSMB to discuss the events and make a determination on the continuation of the trial.

Below are the pre-specified triggers:

The DEFUSE 3 has established the following automatic stopping rules, based on identifying with 95% probability:

- 1) the rate of symptomatic ICH (NIHSS worsening of 4 or more points associated with ICH) in the endovascular group is exceeding 10%
- 2) the rate of 90 day mortality in the endovascular group is exceeding 20%.

If either threshold is crossed, the study will be automatically placed on hold until the investigators and the DSMB can conduct a review of events.

Adverse events (AEs) will be collected, recorded, and analyzed in accordance with Section 3.11 below.

Safety oversight for this study will be provided by both the DSMB and an independent Medical Safety Monitor. Please see Section 3.11 for details.

Patient Population: Four hundred and seventy six acute stroke patients meeting the pre-defined inclusion criteria will be enrolled in the trial. The mean age is anticipated to be 69 years of age. Our targeted planned enrollment breakdown is as follows:

Racial Categories	Ethnic Categories				Total
	Not hispanic or Latino		Hispanic or Latino		
	Female	Male	Female	Male	
American Indian/Alaska Native	2	2	1	1	6
Asian	13	13	1	1	28
Native Hawaiian or Other Pacific Islander	2	3	0	0	5
Black or African American	32	32	1	1	66
White	175	174	11	11	371
Racial Categories: Total of All Subjects	224	224	14	14	476

Imaging core lab: The Stanford imaging core lab has 15 years of experience with MR image storage and processing. It will perform the organization, archiving and blinded analysis of all imaging data collected in DEFUSE 3. They will be responsible for MRI and CT Perfusion image processing and artifact removal and will generate final lesion volumes for all MRI scans performed in the study.

DSA Angiograms sent to the core lab will include a baseline (pre-treatment) and a final angiogram for the territory of treatment. In addition, angiographic images from MRA or CTA will be sent to the core lab. The MRA or CTA will be used to assign a primary arterial lesion (AOL) from non-invasive imaging. The baseline DSA angiogram will also be used to assign a primary arterial occlusive lesion (AOL) and a pre-treatment mTICI score. The final angiogram will have a post-treatment mTICI score assigned.^{22,52} This scoring system defines TICI 2A as partial perfusion of < 50% of the vascular distribution of the occluded artery and 2B as partial perfusion of > 50% of the vascular distribution. The scoring system will use these previously described definitions²²:

- Grade 0 No perfusion
- Grade 1 Antegrade reperfusion past the initial occlusion, but limited distal branch filling with little or slow distal reperfusion
- Grade 2a Antegrade reperfusion of less than half of the occluded target artery previously ischemic territory (eg, in 1 major division of the MCA and its territory)
- Grade 2b Antegrade reperfusion of more than half of the previously occluded target artery ischemic territory (eg, in 2 major divisions of the MCA and their territories)

- Grade 3 Complete antegrade reperfusion of the previously occluded target artery ischemic territory, with absence of visualized occlusion in all distal branches

Two senior neurointerventionalists will perform the angiographic analysis, blinded to the clinical data, MR imaging and CT Perfusion results, and the analysis of the other core lab reader. Any disagreements in the AOL interpretation or the mTICI scores will be adjudicated by common review of those cases and a consensus reading will be applied.

National Data Management Center: Data management and site monitoring will be performed by the StrokeNet National Data Management Center (NDMC) at Medical University of South Carolina (Director, [REDACTED], PhD, see letter of support). The NDMC will create the database and set up the interface on the website (WebDCU™) where clinical site personnel will enter the data into the electronic CRF. Data quality assurance processes include: (1) logic and rule checks built into the database; (2) monitoring by the Data Manager at the NDMC; (3) central monitoring by the statistical programmer at the NDMC; and (4) risk-based source verification monitoring by the Clinical Research Associates. DEFUSE 3 data, including neuroimaging, will be shared in accordance with the StrokeNet data sharing policies. Anonymized neuroimaging will be stored on secure servers at the Stanford Stroke Center with nightly back-up. NINDS Common Data Elements will be used for both clinical and imaging data.

3.10. Description of devices

The following FDA approved thrombectomy devices will be included:

- 1) Trevo Retriever
- 2) Solitaire™ Revascularization Device
- 3) Covidien MindFrame Capture Revascularization Device
- 4) Penumbra thrombectomy system including the following devices and pumps:

Penumbra Aspiration Pump (1115V)	Penumbra System [026, 032, 041]
Penumbra System 054	Penumbra System Separator Flex [026, 032, 041, 054]
Penumbra System MAX	Penumbra Pump MAX
Penumbra System 110 Aspiration Tubing	Penumbra System Reperfusion Catheter ACE64 & ACE68

3.11. Monitoring procedures

The coordination of the DEFUSE 3 Trial operations will be centralized through the following: NIH StrokeNet National Coordinating Center (NCC)/ PI: [REDACTED], MD
University of Cincinnati
[REDACTED]
Cincinnati, Ohio [REDACTED]

Leading the NCC team will be the Project Manager, who will be assigned to coordinate the following study oversight: trial communication required training activities, site assessment and/or initiation visits, collection of trial related regulatory documents, recruitment performance tracking, site monitoring, and performance analysis. Study oversight will be handled according to the Data Monitoring Standard Operating Procedure (SOP Number ADM 19).

DEFUSE 3 will have an independent Data and Safety Monitoring Board (DSMB) appointed by the NIH to oversee study safety. Patients in both study arms will be assessed for the incidence of stroke-related mortality at 90 days, the incidence of symptomatic intracranial hemorrhage at 36 hours from symptom onset (defined as a ≥ 4 point worsening of immediate pre-deterioration NIHSS neurological status vs. post deterioration and associated with brain hemorrhage), and the incidence of significant neurologic deterioration prior to discharge (defined as ≥ 4 point worsening of the immediate pre-deterioration NIHSS neurological status vs. post deterioration and not attributed to sedation). In the endovascular arm patients will be assessed for intra-procedural complications including: intra-procedural mortality, vessel perforation, arterial dissection, access site complication requiring surgical repair or blood transfusion, embolization and device failure. SAEs will be reported within 24 hours of awareness of the event.

The DSMB will meet in person or by teleconference, on a semi-annual basis, to monitor the cumulative safety data during participant follow-up. In no instance will more than 12 months elapse between DSMB reviews of cumulative safety data after the first participant has been randomized. The DSMB will monitor the study according to the guidelines specified in the study protocol and the operating procedures established at the initial meeting, unless the DSMB determines during the course of the trial that modification of the guidelines is in the best interest of the study and its participants.

Independent Medical Safety Monitor:

In addition to the DSMB, Dr. [REDACTED] has been appointed as the independent Medical Safety Monitor (MSM) for DEFUSE 3. Dr. [REDACTED] is not involved in the study and has no conflict of interest. He will be responsible for ongoing monitoring of reports of SAEs submitted by the clinical centers in real time to ensure good clinical practice and to identify safety concerns quickly. Dr. [REDACTED] may suggest protocol modifications to prevent the occurrence of particular AEs, e.g., modifying the protocol to require frequent measurement of laboratory values predictive of the event or to improve expeditious identification of SAEs. In the event of unexpected SAEs or an unduly high rate of SAEs, Dr. [REDACTED] will promptly contact the DSMB Liaison who will notify the DSMB Chair. In the event that he is unavailable for an extended period of time (i.e., extended vacation, sabbatical, illness, etc.), a back-up MSM will be nominated by the study PI and approved by the DSMB.

Adverse Event Reporting

Consideration of adverse events will hereafter consist of adverse events, serious adverse events, and adverse device effects, including anticipated adverse device effects and unanticipated adverse device effects.

- Adverse event (AE) is defined as any untoward/undesirable clinical occurrence in a clinical investigation of a subject which does not necessarily have a causal relationship with the treatment under investigation. An Adverse Event can therefore be any unfavorable and/or unintended sign, symptom, or disease temporally associated with the use of a device product, whether or not considered related to the device product. Only abnormal laboratory values that are deemed clinically significant by the investigator will be classified as adverse events.

- Serious adverse event (SAE) is defined as any untoward/undesirable adverse experience that results in any of the following outcomes: 1) death; 2) a life-threatening adverse experience; 3) inpatient hospitalization or prolongation of existing hospitalization; 4) a permanent/persistent or significant disability/incapacity or a congenital anomaly/birth defect; 5) important medical events that may not result in death, be life-threatening, or require hospitalization may be considered a serious adverse event when, based upon appropriate medical judgment, they may jeopardize the subject and may require medical or surgical intervention to prevent one of the outcomes listed in this definition. This category includes the use of intra-arterial thrombolytics and/or intracranial stents.
- Anticipated adverse device effect (AADE) is defined as any adverse effect related to the device or procedure, which is identified in the protocol or the IFU for the device.
- Unanticipated Adverse Device Effects (UADEs) is defined as any serious adverse effect on health or safety or any life-threatening problem or death caused by, or associated with a device, if that effect, problem, or death was not previously identified in nature, severity, or degree of incidence in the investigational plan or application, or any other unanticipated serious problem associated with a device that relates to the rights, safety, or welfare of subjects.

Reports of UADEs will be made to the FDA within 10 days of receiving notification of the UADE (as required in 21 CFR 812.18p (b)(1)).

Safety Monitoring

The MSM will monitor all AE reports to identify and trend all events that would require temporary discontinuation of study enrollment, to fully characterize device safety, to modify the study protocol, or to terminate the study.

Reporting Procedures for All Adverse Events

All Adverse Events, whether or not attributed to the study and/or the devices, observed by the investigator or reported by the subject, will be recorded from the time of randomization through Day 5 or discharge, whichever is earlier. All SAEs will be recorded through Day 90.

The following attributes will be assigned by the reporting investigator:

1. Description of event
2. Date of onset
3. Date of resolution (if applicable)
4. Seriousness
5. Relationship to the study device and/or procedure(s)
6. Severity
7. Action(s) taken
8. Outcome(s)

Severity is defined as a measure of the intensity of a reaction, effect or experience. The measurement(s) are described as mild, moderate, severe, life threatening or death. The event itself, however, may be of relative minor medical significance. The severity of Adverse Events is assessed according to the following index scale:

- **Mild**
asymptomatic or mild symptoms; clinical or diagnostic observations only; intervention not indicated
- **Moderate**
minimal, local or noninvasive intervention indicated; limiting age-appropriate instrumental Activities of Daily Living.
- **Severe**
medically significant but not immediately life-threatening; hospitalization or prolongation of hospitalization indicated; disabling; limiting self care Activities of Daily Living.
- **Life-threatening consequences;**
urgent intervention indicated
- **Death** related to AE

The relationship of an AE to the study device or procedure will be graded as follows:

- Unrelated
- Unlikely
- Reasonable possibility
- Definitely

Serious Adverse Events All Serious Adverse Events including deaths will be reported to the MSM, the Central Institutional Review Board (IRB) and the FDA, as required.

4. **INVESTIGATOR'S AGREEMENT**

As this study will be carried out by the NIH StrokeNet, the names of the specific sites and investigators are not yet available. Investigator's agreements for key investigators at the coordinating site are included.

All investigators will be required to sign the following agreement:

INVESTIGATOR AGREEMENT FOR THE CLINICAL INVESTIGATION OF THE DEFUSE 3 TRIAL

I _____ agree to participate as an Investigator on the DEFUSE 3 trial.

I have been provided a copy of the following Food and Drug Administration (FDA) regulations: [21 CFR Part 812](#), Investigational Device Exemptions; [21 CFR Part 50](#), Protection of Human Subjects; and [21 CFR Part 54](#), Financial Disclosure by Clinical Investigators.

I agree and/or certify that:

1. I will conduct the clinical investigation in accordance with this agreement, all requirements of the investigational plan, IDE regulations, other applicable regulations of the FDA, and any conditions of approval imposed by my reviewing Institutional Review Board (IRB) or FDA. I agree to abide by all of the responsibilities of Investigators addressed under [21 CFR Part 812](#), Subpart E and Subpart G, including but not limited to the following:
